3.2 Sample Size and Statistical Power

We made the conservative estimate that trial patients have about 50% chance of making another emergency contact within six months; in the absence of intra-cluster correlation (ICC), a sample of 4190 evaluable participants yields 90% power, when using two-sided 5% significance level, of detecting a change in this chance from 50% to <45% or to >55%. The analogous outcome in the SAFER 1^[4] trial indicated an ICC of zero in clusters of participants seen by paramedics from the same ambulance station. To be conservative, we therefore allowed for an ICC of 0.002, and sought 251.6 (calculated from $0.998 \cdot 4190 / (25 - 0.002 \cdot 4190)$) participants per ambulance station, making a total sample size target of 6290.

However, actual recruitment is slightly lower, at 5939 participants, and we will lose approximately 1000 patients that decline to be part of the study. Furthermore, previous experience suggests that we shall also lose about 10% of the remaining patients from analysis because we shall not be able to match them with their routine electronic data on contacts with the NHS. Hence we expect the recruited sample of 5939 participants to yield only 4400 suitable for accurate information linkage. With an ICC of 0.002 and equal cluster sizes, this expected evaluable sample size corresponds to 3260 independent participants, which, in turn, equates to approximately 80% statistical power. In short, the cumulative loss in recruitment, and from dissenting and un-matched patients will reduce the statistical power of SAFER 2 from a conservative 90% to the traditional 80%, even allowing for more intra-cluster correlation than observed in the SAFER 1^[4] trial.

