5.1 Statistical Analysis

This will conform to principles outlined in WWORTH SOP28 Statistics^[5]; specifically, the primary analysis will be by 'treatment allocated', reflecting the pragmatic nature of the trial design where patients are cared for by paramedics based at ambulance stations randomly allocated to deliver intervention or control care.

Primary outcomes comprise a hierarchy relating to further emergency healthcare contacts for falls, as measured by contacts with the 999 service, Emergency Department (ED) or emergency admission to hospital for a further fall, or deaths within six months of the index fall. Important predictors that may affect triage decisions and outcomes, including the distance between incidents and EDs at index fall, patient age and gender, patterns of presentation (eg, whether out-of-hours or not) will be considered as covariates, and included in statistical modelling. We shall also take account of potential confounders such as the sequence of base stations (and their trial allocation) from which paramedics attend patients who fall more than once. The principles used in analysing primary outcomes also apply to quantitative secondary outcomes.

Required analyses include: logistic regression (for binary outcomes); cross-tabulations and risk ratios (for categorical outcomes); and survival analysis, including Cox's proportional hazards models^[10], (for measurement outcomes, such as times to events). Primary outcomes will also be jointly analysed using methods developed for recurrent event analysis^[11-14]. Repeated observations will be analysed in two ways: as 'repeated measures'; and summarised by "area under curve" of HRQoL measures per patient.

Where appropriate, multilevel modelling will be used to estimate clustering effects for stations or centres. The exact number of levels in models will be determined using statistically significant changes in likelihood ratio tests according to the principle of parsimonious parameterisation. Potential covariates to be included in models will be tested; those with an F value of less than 1 (that is, they increase the standard error of the estimate) will be excluded and the analysis recalculated. Binary covariates where almost all cases (>90%) are in one category will also be excluded.

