Residual diagnostics will be used where analyses assume Normality; if the distributions of residuals are markedly non-normal, data transformation or bootstrapping will be considered. Residual analysis will be used to identify outliers; identified outliers will be excluded and the analysis updated. Wherever possible, outcome descriptions, summaries and comparisons will be expressed in accordance with appropriate CONSORT (www.consort-statement.org) guidelines, including estimates with 95% confidence intervals (allowing two-tailed tests at the 5% significance level).

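### The randomised unit, station, stays in the model only if a likelihood ratio test is significant; at the plan's own ICC it will usually be dropped and the 5% error rate exceeded

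*SAP*

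**What the plan says.** SAP section 1 describes a cluster randomised trial of 25 ambulance stations in three centres, with half the stations allocated to the intervention.

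Section 3.2 plans for clustering by station. The earlier trial gave an ICC of zero, but the authors preferred caution: "we therefore allowed for an ICC of 0.002". They carry this value into the expected power: "With an ICC of 0.002 and equal cluster sizes, this expected evaluable sample size corresponds to 3260 independent participants".

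Section 5.1 makes the modelling of clustering conditional: "Where appropriate, multilevel modelling will be used to estimate clustering effects for stations or centres". It then says how the levels are chosen: "The exact number of levels in models will be determined using statistically significant changes in likelihood ratio tests", with parsimony as the guiding principle. Nothing in the section exempts station from the test. No robust variance or station-level analysis is named for the case where the level is removed. The same section extends its approach from the primary outcomes to the quantitative secondary outcomes, and promises "estimates with 95% confidence intervals (allowing two-tailed tests at the 5% significance level").

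**The concern.** In a cluster randomised trial, the variance of the treatment comparison includes the between-station variance because stations were allocated. A non-significant test of that variance does not show it to be zero. With few clusters and a small ICC, the test will miss most of the clustering that matters. At 176 patients per station, even an ICC of 0.002 inflates the variance of the comparison by 35%.

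Under this rule, the primary effect would usually be reported with a standard error that treats patients as independently randomised. P-values and intervals would be too optimistic for the primary outcomes and for the secondary outcomes analysed in the same way. The design and the analysis would also not match: section 3.2 discounts the sample for clustering, and section 5.1 would usually take the discount back. The choice would be settled only once the outcome data had been seen.

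**Working it through.** **Inputs.** From the SAP: 25 stations; ICC 0.002; 4400 evaluable patients; 50% against 45%; two-sided 5%. Assumed, because the SAP does not say: a 12:13 split of stations, equal station sizes (4400/25 = 176), and a likelihood ratio test at 5%. Station means are treated as Normal, with no covariates or strata.

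**The plan's own figures reproduce.**
- Without clustering: n per arm = [1.960·√(2·0.475·0.525) + 1.282·√(0.50·0.50 + 0.45·0.55)]² / 0.05² = 2095 after rounding up, so 4190 in total.
- With clustering: 0.998·4190/(25 − 0.002·4190) = 251.6 per station, and 25·251.6 = 6290.
- After losses: design effect = 1 + (176 − 1)·0.002 = 1.35, and 4400/1.35 = 3259 (stated as 3260). Power with 1630 per arm is 81.6% (stated as approximately 80%).

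**How often station is kept at ICC 0.002.** Let r be the estimated between-station mean square divided by the within-station mean square. For r above 1, the likelihood ratio statistic is close to K(r − 1 − ln r), with K = 25 for maximum likelihood (ML) and K = 23 for restricted maximum likelihood (REML). The product K·r is distributed approximately as 1.35 times a chi-square on 23 df. The cut-off is 3.84 for chi-square on 1 df, or 2.71 for the 50:50 mixture that allows for testing on the boundary.

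| Test | r needed | K·r/1.35 | Station kept |
|---|---|---|---|
| ML, 3.84 | 1.661 | 30.76 | 12.9% |
| REML, 3.84 | 1.694 | 28.86 | 18.5% |
| ML, 2.71 | 1.540 | 28.52 | 19.7% |
| REML, 2.71 | 1.566 | 26.69 | 27.0% |

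Station is therefore dropped in 73% to 87% of trials.

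**Type I error at ICC 0.002.**
- Station dropped: 2·[1 − Φ(1.96/√1.35)] = 2·[1 − Φ(1.687)] = 9.2%.
- Station kept: kept trials are those in which the between-station variance looks large, so they reject only about 1% to 2% of the time.
- Overall, least to most favourable test: 0.871·9.16% + 0.129·1.6% = 8.2%, down to 0.7305·9.16% + 0.2695·1.7% = 7.1%. The spread includes the choice between a Normal and a t reference when station is kept.
- Simulation of 200,000 null trials under the same assumptions gave 7.2% to 8.3%.
- Station always accounted for (t test on station means, 23 df): 5.0%. A random intercept that is always kept gave 4.4% with a t reference and 5.6% with a Normal reference.

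**Interval width when station is dropped.** 1/√1.35 = 0.861, so intervals are about 14% too narrow.

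**Other values of the true ICC** (simulation):

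| ICC | Design effect | Station kept | Error under the rule | Error if always ignored |
|---|---|---|---|---|
| 0 | 1.00 | 1–4% | 4.9–5.0% | 5% |
| 0.001 | 1.175 | 5–13% | 6.4–6.9% | 7% |
| 0.002 | 1.35 | 13–27% | 7.2–8.3% | 9% |
| 0.005 | 1.875 | 51–69% | 6.9–9.1% | 15% |
| 0.01 | 2.75 | 89–95% | 5.5–7.3% | 24% |
| 0.02 | 4.50 | over 99% | 5.0–6.3% | 36% |

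At 0.02 station is almost always kept. What remains above 5% there comes from using a Normal rather than a t reference with 25 clusters, not from the selection rule.

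**The case against.** The only empirical evidence in the SAP is an ICC of zero from the earlier trial, and 0.002 is a deliberate allowance, not an estimate. If the true ICC is zero, the rule costs nothing. If it is 0.01 or more, the test will nearly always find it. The excess is moderate even at 0.002: against an always-kept model with a Normal reference (5.6%), it is about 1.6 to 2.7 percentage points. Section 1 commits to the CONSORT statement for cluster trials, and section 5.1 defers to a statistics SOP that is not shown and may contain a rule on clustering. The sentence on levels might also be meant only to decide whether centre is added above station.

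Much of this is fair as a limit on size. That station is usually dropped holds for a true ICC from 0 up to about 0.003, not above about 0.005. Nor can the figures be carried over to the questionnaire outcomes, which have fewer patients per station and no stated ICC.

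It does not rescue the rule. An estimate of zero does not establish a true value of zero, and the plan itself declined to rely on it. The test is weakest between zero and 0.005, where the planning value lies. A general reference to a reporting guideline or to an SOP does not override an explicit rule, and the text names stations as one of the levels to which the rule applies.

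**Conclusion.** The concern holds. As written, section 5.1 lets a low-powered test remove the randomised unit from the primary analysis. At the plan's own ICC of 0.002, station would be dropped in about three quarters or more of trials. The true two-sided error would be about 7% to 8% instead of 5%, and 9.2% in the trials where station is dropped. Error was above 5% at every positive ICC examined from 0.001 to 0.01, and at its nominal level when the ICC was exactly zero.

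The exact figures rest on equal stations of 176, a 12:13 split, a 5% likelihood ratio test, Normal station means and no covariates. The direction does not depend on which of the four versions of the test is used. Because the rule governs the validity of the primary inference and is easily corrected, it must be changed before analysis.

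**What to change.** Replace the sentence on the number of levels in section 5.1 with wording such as:

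> Every comparison between groups will account for randomised station, by a random effect, a shared frailty or a cluster-robust variance, whatever its statistical significance, with a small-sample correction for 25 clusters. Likelihood ratio tests may be used only to decide on levels other than station.

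The SAP should name the correction for each model. A t reference on about 23 df (25 − 2) is one option. Kenward-Roger is another, but only for the linear mixed models. The rule should cover the logistic, risk-ratio, Cox and recurrent-event analyses. For consistency, the bootstrap in section 5.2 should resample stations and not individual patients.

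The cost is a change of wording; no new data are needed. Where station would have been dropped at an ICC of 0.002, intervals widen by about 16% (√1.35 = 1.16), which the 3260 independent participants in section 3.2 already allow for. A t reference on 23 df widens them by a further 6% or so (2.069/1.960), which the Normal-based power figure does not include.

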5.2 Health Economic Analysis

This will estimate costs of providing the new intervention, and consequences for the NHS (for instance, ED attendances, inpatient admissions) and personal social services. Data on the use of the health service resources will be collected for each patient using routine ambulance service and hospital records. Costs will then be calculated using unit-costs estimated through a micro-costing study within the trial. Direct costs to the NHS will be assessed using data logged as a part of routine practice and from resource utilisation recording sheets, together with reference to patient records and discussions with relevant finance staff.

SF6D scores (derived from SF12 scores) will also be used to estimate the quality adjusted life years (QALYs) gained from the intervention, and an incremental cost-per-QALY calculated. These ratios will be presented along with their associated Cost-effectiveness Acceptability Curves (CEAC). Sensitivity analyses will be undertaken to assess the robustness of results to changes in the configuration of the intervention and other health service costs. We aim to publish economic results alongside clinical results where possible (for instance, in the BMJ format of pairs of companion papers).

The Senior Trial Economist is responsible for the health economic analysis, which will generally adopt approaches employed in the main analysis of clinical data. Specifically: .

- Analysis will be by 'treatment allocated' when generating baseline findings, with inclusive analysis by treatment received or exclusive analysis of treatment per-protocol being used for sensitivity analysis when also undertaken in reporting clinical findings
- Addressing uncertainty by applying bootstrapping for CEACs and confidence intervals^[15-17].
- Using a range of time-horizons to estimate the effectiveness and cost-effectiveness of the intervention.
- Applying appropriate discount rates to costs and benefits, as required by NICE; applying appropriate threshold Incremental Cost-effectiveness Ratios (ICER), such as the £20,000 and £30,000 thresholds used by NICE, in cost-per-QALY calculations.

5.3 Qualitative Analysis

All interviews and focus groups, with the permission of participants, will be recorded and transcribed. As this is a team-based project involving collection of data in multiple sites, maintaining consistency in data collection and transcription is crucial. The qualitative analysis co-ordinator will set up a data management system consisting of instructions on converting raw data to computer files (in the form of a transcription protocol), organising data storage, data archiving steps and a data management checklist. The transcription protocol will ensure that standard conventions are adopted throughout the transcription process, and that a standard presentation format is used. Each transcript will be quality assured by the relevant researcher.

Following transcription, participants in the paramedic and service provider focus groups will be given the opportunity to review the anonymised transcripts and state whether they agree with the contents or wish to amend their quotes.

The data will be analysed thematically using the framework analysis approach for applied policy research^[18]. This is a systematic, dynamic and transparent method of analysis, which generates themes from the original accounts of participants^[19]. In the analysis the data is sifted, charted and sorted in accordance with key issues and themes using five steps: familiarisation; identifying a thematic framework; indexing, charting; and mapping and interpretation.

All data analysis will be carried out independently by two researchers, who will then meet to discuss and agree final coding and interpretation. Analysis will be conducted using NVivo. When reporting the results, we will ensure that the anonymity of responders is preserved and that no quote can be attributed to a particular individual.

Section 6: INTERIM & FURTHER ANALYSES

Patients will be recruited over a 15 month period and followed up for six months. The trial will end and be analysed after the last six month follow-up contact with any patient in the trial. No formal interim analyses of the trial outcomes, and no subgroup analyses, are planned within the trial.

6.1 Non-Consenter Analysis

Study patients will be compared with eligible patients who have not consented to the study in terms of age, gender, date and time of index call, on-scene time, main condition code and disposition by appropriate significance tests.

6.2 Non-Respondent Analysis

Study patients who have returned the study questionnaire will be compared with those who have not return the questionnaire by the same parameters of the non-consenter analysis. In addition, those responding to the questionnaire will also be compared to those not returning the questionnaire in terms of the primary outcomes.

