3.1 Data Sources & Collection

Our primary outcome is “further emergency healthcare contacts (999 call or Emergency Department (ED) attendance or hospital admission) or death for any reason and for falls per recruited faller, and time to first contact or death” for six months following the index call. This CRT does not approach participants at the point of treatment, because they may be in distress and unable to give informed consent, but seeks instead retrospective consent to follow up through routine medical records and by postal questionnaire. We planned to follow-up all our patients anonymously in order to achieve the primary outcome for our target sample size. In Wales, arrangements for this process are already in place through the existing SAIL (Secure Anonymised Information Linkage) Database, and our application for permission through the Information Governance Review Panel has been granted. We applied to the NIGB Ethics and Confidentiality Committee for permission to follow-up our patients anonymously through the Information Centre in England and permission has been granted for this process. Conditional to this permission, people who have clearly dissented to identifiable follow-up must be excluded from the study. For clarity, if a patient has at any time declined to be part of the study (either in returning a consent form or orally on the telephone) they will be removed from the study.

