3.3 Missing Data

General Principles

As per WWORTH SOP28 Statistics^[5], we shall adopt a consistent approach to missing data relating to both effectiveness and cost-effectiveness except where individual outcome measures require some variation in that approach. We shall exclude participants without follow-up data, and, for each variable, summarise the frequency of missing data, which directly influences the sample size in, and hence the statistical power of, some analyses. If there is reason to suspect that data are not Missing Completely At Random (MCAR), the trial statistician and chief investigator will discuss the findings. If there is no reason to suspect that data are not MCAR, we shall use appropriate imputation methods to mitigate the problem of missing data.

Internal imputation of HRQoL data at a particular data collection point

None of the questionnaires (SF-12, derived SF-6D, or Modified Falls Efficacy Scale (mFES)^[6]) has an official algorithm for imputing individually missing answers. Some patients may have particular reasons for missing some of the questionnaire items, and it is unlikely that a plausible model for conditional Missing At Random can be established even on a case-by-case basis. Nevertheless, to minimise missing values and use available information, any such missing values within patient interviews will be completed by imputation^[7] within the reduced dataset of individual responses to questions in the three measures, using the regression or expectation maximization (EM) algorithms of the Missing Value Analysis module within SPSS. Scale scores will then be calculated according to the relevant instructions for the measure. The use of multiple imputation methods will be considered if the incidence of missing data is high.

External imputation of HRQoL data scores

If a participant is dead at the data collection point, the SF-6D score will be taken as zero. To avoid outliers, SF-12 and mFES scores will be taken as the minimum value observed for that measure in the relevant treatment group

Otherwise, missing summary scale and subscale scores will be imputed by regression from all available values of that score at other data points and the allocated treatment group. Further predictors (eg gender, age, current hospitalisation) may be included, unless they are already used as covariates in the main analysis

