3.4 Withdrawals

Patients can withdraw from the study whenever they wish, and do not have to give a reason, although any reasons given must be documented. Their subsequent treatment will not be affected in any way. Patients may also withdraw from the questionnaire element of the study but be retained for other follow up. Any patients lost must be traced and documented whenever possible.

Wherever possible, data missing because of withdrawal will be imputed from available data.

Section 4: LINKS BETWEEN OBJECTIVES & OUTCOMES

4.1 Trial Objective 1 'Compare costs, processes and outcomes of care between experimental and control groups'

Objective 1a Patient Outcomes

- | | | |
|---|---|--------------------------|
| 1 | Number of further reported contacts or deaths | [primary outcome] |
| 2 | Time to the first reported contact or death | [primary outcome] |

Primary outcomes will be analysed using the hierarchy of outcomes (comprising 999 calls, ED attendances, emergency admissions, and death) established in SAFER1^[4].

- 3 Injuries related to further falls **[secondary outcome]**
This will be summarised by cross-tabulation of the numbers and proportions in each study group, split by types of injuries.
- 4 Health-related Quality of Life **[secondary outcome]**
This is measured by SF-12 and derived SF-6D, and will be assessed and summarised at one month and six months.
- 5 Satisfaction **[secondary outcome]**
This is measured by the Quality of Care Monitor, and will be assessed and summarised at one month.
- 6 Psychological status **[secondary outcome]**
This is measured by the mFES, and will be assessed and summarised at one month and six months.
- 7 Change in place of residence at six months **[secondary outcome]**

Objective 1b Processes of Care

- 1 Pathway of care **[secondary outcome]**
This is measured by health and social care contacts associated with the index fall and during follow-up period, split by types of contacts and adjusted by covariates.
- 2 Ambulance service operational indicators **[secondary outcomes]**
These comprise episode of care and job cycle times, adjusted by covariates.
- 3 Protocol compliance **[secondary outcome]**
This will be measured by a series of data items related to protocol compliance (such as the completion of clinical documentation; referral processes).

Objective 1c Cost of Care **[secondary outcome]**

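### The non-respondent analysis in Section 6.2 counts patients who died before a questionnaire was due as non-respondents with a primary event, which pushes the comparison towards non-respondents doing worse

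*SAP*

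**What the plan says.** Section 6.2 sets up two groups: "Study patients who have returned the study questionnaire will be compared with those who have not return the questionnaire". After the descriptive comparison on patient and call characteristics, it adds that "those responding to the questionnaire will also be compared to those not returning the questionnaire in terms of the primary outcomes". It does not limit the comparison to patients alive when the questionnaire was due, does not class deaths separately, and does not say whether the one-month or the six-month questionnaire defines a respondent.

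Death is part of the primary outcome wherever the SAP defines it:
- Section 3.1: "further emergency healthcare contacts (999 call or Emergency Department (ED) attendance or hospital admission) or death for any reason".
- Section 4.1, Objective 1a: "Number of further reported contacts or deaths" and "Time to the first reported contact or death".
- Section 5.1: "or deaths within six months of the index fall".

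There are two questionnaire waves. In Section 4.1, quality of life and fear of falling "will be assessed and summarised at one month and six months"; satisfaction is measured at one month only.

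Section 3.3 treats death differently from other missing questionnaire data: "If a participant is dead at the data collection point, the SF-6D score will be taken as zero". SF-12 and mFES then take the lowest value observed in the treatment group. Only the remaining missing scores are imputed by regression.

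**The concern.** Someone who has died cannot return a questionnaire. If the death falls inside the six-month window, that person also has the primary event. Under Section 6.2 every such patient enters the non-returner group as an event, and none can enter the returner group. Part of the difference then follows from how the groups are defined and says nothing about how living patients respond. For contact counts there is a second distortion: early death shortens the time in which contacts can occur.

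Section 6.2 is the only planned comparison of questionnaire respondents with non-respondents on outcomes. A reader would naturally use it to judge whether the quality-of-life, fear-of-falling and satisfaction results are distorted by non-response. It may also inform the discussion that Section 3.3 requires when data are suspected not to be missing completely at random, although the SAP does not link the two. A gap produced by deaths could suggest selective response among survivors where there is none, or hide a real difference in the other direction.

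**Working it through.** **The plan's figures.** Section 6.2 states no figure. Two inputs come from Section 3.2: about 4400 evaluable patients and a 50% six-month event risk. The first is consistent with its source: (5939 − 1000) × 0.9 = 4445, stated as 4400. The second belongs to a sample-size calculation that reproduces: 50% against 45%, two-sided 5%, 90% power gives 2 × 2095 = 4190.

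**Assumptions.** Mortality before the questionnaire and response among survivors are not in the SAP and are varied below. Response among survivors is taken as unrelated to outcome, so the true response bias is zero.

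**Formula.** Let N be the patients, D the deaths before the due date, L = N − D the survivors, r the survivors' response rate and p their event risk.
- Returners: rL patients, event proportion p.
- Non-returners: (1 − r)L + D patients, with p(1 − r)L + D events.
- Artefact = (1 − p) × D / [D + (1 − r)L].

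**Main case: N = 4400, r = 50%, p = 50%, six-month questionnaire.**

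| Dead before due date | Returners | Non-returners | Events in non-returners | Proportion | Gap from 50.0% |
|---|---|---|---|---|---|
| 2.5% (110) | 2145 | 2145 + 110 = 2255 | 1072.5 + 110 = 1182.5 | 52.4% | 2.4 points |
| 5% (220) | 2090 | 2090 + 220 = 2310 | 1045 + 220 = 1265 | 54.8% | 4.8 points |
| 10% (440) | 1980 | 1980 + 440 = 2420 | 990 + 440 = 1430 | 59.1% | 9.1 points |

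At 5% dead, ignoring clustering, the standard error is √(0.25/2090 + 0.2477/2310) = 0.0151, so z is about 3.2 and p about 0.002.

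**Sensitivity to the assumptions.**
- Lower response (5% dead, r = 25%): non-returners 3135 + 220 = 3355, events 1567.5 + 220 = 1787.5, proportion 53.3%. The gap is 3.3 points, z about 1.85, p about 0.06.
- Few deaths (1%, r = 50%), as might hold at one month: (1089 + 44)/2222 = 51.0%. The gap is 1.0 point, not significant.
- Lower event risk in survivors (p = 30%, 5% dead, r = 50%): 0.7 × 220/2310 = 6.7 points.
- Overall event rate, deaths included, held at 50%: survivors' risk is (0.50 − 0.05)/0.95 = 47.4% at 5% dead. With r = 50% the non-returners have 52.4%, a gap of 5.0 points, significant with about 91% probability. At 2% dead and r from 30% to 70%, the gap is 1.4 to 3.2 points, significant with 14% to 52% probability.

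**With the change.** Among patients alive on the due date D = 0, so the artefact is zero under the same assumption.

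**The case against.** Several points on the other side have force.

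- **The hierarchy.** Sections 4.1 and 5.1 analyse the primary outcomes as a hierarchy of 999 calls, ED attendances, emergency admissions and death. If Section 6.2 is reported level by level, death is visible as its own level and the non-fatal levels are not events by definition for the dead. A reader might infer that the analysis can never separate death from response bias. The SAP does not support that, because it does not say that only a pooled composite will be shown. It does not commit to showing the levels in Section 6.2 either, and shortened time at risk still affects the contact levels.
- **Size.** A reader might infer that the analysis is bound to report significant response bias. Only the direction of the push on the composite and time-to-first-event outcomes is fixed. With low mortality or low response the gap can be small and non-significant.
- **Denominator.** The 4400 are patients linkable to routine data. The SAP does not say how many of them were sent a questionnaire, so the z values are illustrative. The gap in points does not depend on N.
- **The 5-point target effect.** The artefact can be of similar size, but the target is a difference between study groups and this is a difference between returners and non-returners. The two should not be equated, and no treatment estimate is stated to depend on Section 6.2.
- **Death scoring.** A reader might infer that Section 3.3 already deals with these deaths for every questionnaire outcome. It does so for SF-6D, SF-12 and mFES only. Satisfaction has no death rule, so for that outcome patients who died first are missing, and counting them as such is a fair description.
- **Protocol detail.** Mailing procedures may be in the protocol, which is not at hand. The groups and outcomes to be compared, however, are fixed in this SAP section.

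These points limit the size and reach of the problem. None of them removes it.

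**Conclusion.** The point stands in a limited form. Followed as written, Section 6.2 places every death before the due date among the non-returners as an event, whereas Section 3.3 treats the same deaths as a state distinct from other missing scores on three of the measures. The size rests on mortality and response rates that the SAP does not give, so the tabulated gaps are illustrations and not predictions. At one month only deaths before that questionnaire are forced into the non-returner group; later deaths can occur among returners. The consequence is a contaminated reading of response bias in the questionnaire outcomes. The documents give no ground for saying that the treatment comparison on the primary outcome changes. This is a worthwhile correction to a supportive analysis.

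**What to change.** In Section 6.2:

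1. Make the comparison separately for the one-month and the six-month questionnaire, and state which return defines a respondent in each.
2. Restrict each comparison to patients alive on the date that questionnaire was due. At six months, compare on the contact outcomes, since deaths up to that date have been set aside.
3. Report deaths before each due date as a separate row by study group, outside the non-respondents.
4. Note that such deaths are scored under Section 3.3 for SF-6D, SF-12 and mFES, but remain missing for satisfaction.

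The cost is a few sentences. Dates of death are already needed for time to first contact or death, and Section 6.2 already requires questionnaire status to be joined to outcomes. The restricted comparison describes living patients only, which is why the row of deaths should appear beside it.
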